### **Interventions**

### Diet-induced weight loss plus exercise

#### Months 0 -6

There will be two individual sessions per month and 2 group sessions per month for the first 6 months. The behavioral sessions will focus on awareness of changing eating habits to lower caloric intake. Educational content information regarding what food changes to make, how to make them, and why they are important will be clearly explained and discussed with participants and significant others. Each group session will include problem solving, review of a specific food topic, and tasting of several well-balanced, low-fat, nutritious foods prepared with widely available ingredients. During the individual sessions, the counselor will review individual progress, solve problems, answer questions, and set goals. During the initial individual session, the nutrition counselor will give the participant a weight history background questionnaire. The major emphasis for Period 1 is to enhance participant awareness of the importance and the need to change eating habits, i.e. lower caloric intake for weight loss. Each participant should be given the opportunity to practice skills using goal setting in a stepwise approach. Participants will follow a weekly menu plan which will incorporate meal replacements into their diet plan. Lean Shakes, a General Nutrition Center (GNC), product will be the meal replacement used. Participants may replace the Lean Shakes with a healthy, low-calorie meal of their choice, such as Lean Cuisine. Motivation and encouragement through the combined efforts of the nutrition counselor, the participant, significant others and the nutrition staff will enhance adherence.

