### Months 13-18

Period 3 will emphasize weight management over time, with 1 monthly individual contact. Weight loss can continue throughout the intervention, provided the participant wants to and has not reached a level associated with health hazards; i.e. a 20% body weight loss at 6 months or >30% at 12 months. Participants will continue to follow a

weekly menu plan with recipes using traditional foods and the option to incorporate meal replacements.

The exercise intervention will cover an 18-month period. The exercise program will consist of a 15-minute aerobic phase, a 20-minute strength-training phase, a second 15-minute aerobic phase, and a 10-minute cool-down phase. These sixty-minute exercise sessions will be conducted three days per week (two days/week will be center based). Each participant will be prescribed an individual walking prescription by the exercise leader, which will be adjusted accordingly, as each participant progresses throughout the 18 months. The exercise will be of moderate intensity. Alternate forms of aerobic exercise, such as but not limited to stationary bike, elliptical trainer, or treadmill walking, can be used in place of over-ground walking. This choice could be based on participant preference, the limitations of the exercise facility, or the participant's pain level. To motivate participants to be physically active intervention staff will plan an optional fun walk. The walk will take place at Wake Forest University. Participants do not have to participate in the walk in order to be in the study. If a participant chooses to participate in the walk they will be asked to sign a waiver.

Intervention Locations: *Forsyth County:* The diet and exercise classes will be offered at a number of sites within Winston-Salem. Participants will be allowed to pick the location that is most convenient for them to attend. Classes will take place at the Clinical Research Center on the Wake Forest University Campus, at St. Peter's World Outreach Center, and at Smiley's Fitness. *Haywood County:* The diet and exercise classes will be held at the Haywood Regional Health & Fitness Center in Waynesville, NC. *Johnston County:* The diet and exercise classes will be held at the Clayton Community Center and the Johnston Medical Mall. Participants will also be allowed to exercise outdoors at the intervention sites when the weather permits. Staff will schedule set times when outdoor walking will be allowed.

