# Primary Aim.

The primary hypothesis of long-term reduced WOMAC pain at 18 months will be tested based on a two-tailed significance level of 0.05 using contrast statements from a repeated measures mixed linear model with time (6, 18 mos), randomization arm (D+E vs control), and the interaction, which adjusts the means at each time point for potential missing data bias (Laird and Ware). Intervention-effect estimates will be further adjusted for baseline pain values, BMI, county, and gender; analysis will match design, so the variance estimate will not be biased. Participant ID number will be included as a random effect to control for within-subject variability, and the longitudinal model will use an unstructured covariance matrix. In the unlikely event the model does not converge, a first-order autoregressive (AR[1]) covariance structure will be fit instead. Maximum-likelihood techniques will estimate parameters, as in the IDEA trial (Messier et al). Preliminary analyses will be conducted to check the shape of the distributions and variances between groups and as a function of the covariates. Regression diagnostics and residual plots will help to find appropriate transformations, if necessary. We will include exploratory analyses of subgroups, defined by gender, age (<70 vs  $\geq$ 70 years), baseline BMI (27.0-34.9, 35-44.9,  $\geq$ 45 kg/m^2), county, and race to determine any differential pain responses.

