## **Primary Outcomes**

Aim 1. A total sample of 820 (410/group) will provide 94% statistical power to detect differences  $\geq 15\%$  in pain at the 2-sided 0.05 significance level with 80% retention (2-sample t-test, Nquery Advisor). Based on ADAPT (Messier et al). The D+E group in IDEA reduced pain by an average of 51%. This approach utilizes the conditional variance approach of Borm et al. for the estimation of power for ANCOVA models using group standard deviation  $\sigma = 3.50$ , Pearson correlation between baseline and 18-month pain score of  $\rho = 0.4$  for a conditional standard deviation  $\sigma_c = 3.21$  ( $\sigma_c = \sqrt{1 - \rho^2} \times \sigma$ ), and 18-month treatment WOMAC pain means ~D+E

Table 2: Detectable absolute a         410/group, 80% retention, 85%         18M values is p .	modifications in retention and treatment effect are				
Variable	Anticipated 18m Control mean*	Standard Deviation	ρ	D+E Mean (% change from C)	presented in Table 1. Correlation
WOMAC Function	17.5	11.5	0.6	15.3 (-12.3%)	between baseline
Mobility: 6-Minute Walk (m)	509	90.7	0.7	524 (3.0%)	and 18 month pain
SF-36 Physical Score (0-100)	42.0	10.1	0.5	44.1 (4.9%)	values are

= 5.03 vs E-only control = 5.92 ( $\Delta$  = -0.887). Variations of anticipated power due to

WOMAC Function17.511.50.615.3 (-12.3%)between baselineMobility: 6-Minute Walk (m)50990.70.7524 (3.0%)and 18 month painSF-36 Physical Score (0-100)42.010.10.544.1 (4.9%)values areestimated from the IDEA trial, while anticipated treatment effects and standard deviation for painwere obtained using weighted averages of D+E and non-D+E treatments from the ADAPT andIDEA studies, with some attenuation of the anticipated treatment effect due to the pragmatic

nature of WE-CAN (Table 1).

 Table 1: Power estimates for WOMAC pain, assuming baseline N=820, correlation between BL and 18 months=0.4, and common group SD = 3.50.

18 month Control Mean WOMAC	18 Month D+E WOMAC Pain (% difference from	18-Month Retention						
Pain	Control)	70%	75%	80%	85%			
		Power						
	5.15 (13%)	81%	84%	86%	88%			
5.00	5.03 (15%)	91%	92%	94%	95%			
5.92	4.91 (17%)	96%	97%	97%	98%			

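### Group delivery in the D+E arm is not reflected in the primary model or in the 94% power; a class-level sensitivity analysis and a qualified power statement are needed

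*Combined protocol and SAP*

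**What the plan says.** **Delivery.** In the D+E arm, the plan for months 0-6 states: "There will be two individual sessions per month and 2 group sessions per month for the first 6 months". Months 7-12 bring one group and one individual diet session a month, and months 13-18 one individual contact a month. Exercise runs for all 18 months. The exercise description makes two of the three weekly sessions centre based. On location: "The diet and exercise classes will be offered at a number of sites within Winston-Salem"; Haywood and Johnston have named venues too. Under Nutrition & Health Intervention, controls have five group meetings in 18 months and otherwise receive packets, webinars, texts or emails.

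**Analysis.** Randomization is individual, stratified by BMI and gender, with county also used. The Primary Aim model has arm, time and their interaction, adjusts for baseline pain, BMI, county and gender, and has a participant random effect. Directly after the covariate list it says: "analysis will match design, so the variance estimate will not be biased". The Secondary Aims models have the same structure. No section mentions class, interventionist, venue, an ICC or a design effect.

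**Power.** Primary Outcomes states: "A total sample of 820 (410/group) will provide 94% statistical power to detect differences" of 15% or more, from a two-sample t-test with a conditional standard deviation.

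**The concern.** This is a partially nested design. Participants are randomized one by one, but in one arm the treatment then reaches them in groups with a common leader and shared peers. Outcomes of D+E participants in the same class may therefore be correlated, while controls have much less opportunity for this.

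The participant random effect handles repeated measures within a person, not correlation between people. County as a fixed main effect removes county differences common to both arms. It does not remove class or leader effects that arise only in D+E.

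If such effects exist, the planned standard error for the 18-month contrast is too small, the confidence interval too narrow and the stated power too high. This matters because the trial is meant to be a model for other communities, which would have other classes and leaders.

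**Working it through.** **Inputs from Primary Outcomes:** 410 per arm; test conditions "at the 2-sided 0.05 significance level with 80% retention (2-sample t-test, Nquery Advisor"; "correlation between BL and 18 months=0.4, and common group SD = 3.50"; 18-month means "5.03 vs E-only control = 5.92", difference 0.887.

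**Assumptions, not in the documents:** m = 8 to 20 retained participants per class; ICC 0.01 to 0.05; equal class sizes; clustering in D+E only.

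**Step 1: reproduce the stated power.**
- Conditional SD = 3.50 × √(1 − 0.4²) = 3.208.
- n = 410 × 0.80 = 328 per arm.
- SE = 3.208 × √(2/328) = 0.2505, and 0.887/0.2505 = 3.541.
- Power = Φ(3.541 − 1.960) = 94.3%.

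The 94% is therefore correct arithmetic for independent participants, that is, a design effect of 1.

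**Step 2: allow clustering in D+E.**
- DE = 1 + (m − 1) × ICC.
- SE = 3.208 × √[(1 + DE)/328].
- Size of the unadjusted test when the average effect is zero = 2 × [1 − Φ(1.960 × √(2/(1 + DE)))].
- Normal-approximation power = Φ(0.887/SE − 1.960).
- For the adjusted test, Satterthwaite df = (1 + DE)² / [DE²/(k − 1) + 1/327], with k = 328/m classes; power then comes from the noncentral t distribution.

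**Worked case, m = 20, ICC 0.05:**
- DE = 1.95 and SE = 3.208 × √(2.95/328) = 0.3042.
- Size: 1.960 × √(2/2.95) = 1.614, giving 10.7%.
- Normal power: Φ(2.916 − 1.960) = 83.0%.
- k = 16.4, df = 8.70/(3.80/15.4 + 1/327) = 34.8, critical t = 2.03, power 80.9%.
- Interval width ratio = (0.3042 × 2.03)/(0.2505 × 1.96) = 1.26.

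| m | ICC | DE | Size of unadjusted test | Power, normal | Power, small-sample df | Interval wider by |
|---|---|---|---|---|---|---|
| 8 | 0.01 | 1.07 | 5.4% | 93.6% | 93.3% | 3% |
| 8 | 0.02 | 1.14 | 5.8% | 92.8% | 92.5% | 4% |
| 8 | 0.05 | 1.35 | 7.1% | 90.4% | 90.0% | 10% |
| 15 | 0.01 | 1.14 | 5.8% | 92.8% | 92.2% | 5% |
| 15 | 0.02 | 1.28 | 6.6% | 91.3% | 90.4% | 9% |
| 15 | 0.05 | 1.70 | 9.2% | 86.2% | 84.9% | 19% |
| 20 | 0.01 | 1.19 | 6.1% | 92.3% | 91.3% | 7% |
| 20 | 0.02 | 1.38 | 7.2% | 90.1% | 88.8% | 12% |
| 20 | 0.05 | 1.95 | 10.7% | 83.0% | 80.9% | 26% |

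By the normal approximation, power falls below 90% once DE exceeds about 1.39: ICC about 0.043, 0.028 or 0.020 for classes of 10, 15 or 20.

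**The case against.** **The variance sentence is not a false statement.** A reader might infer that it denies any clustering. It follows the covariate list, and BMI, gender and county are the factors used in randomization. The natural reading is that the model includes those factors, which is sound. What stands is that, left unqualified, it gives no assurance for group delivery.

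**Inflation of the primary test is not certain.** Because randomization is individual, a programme with no effect on anyone leaves outcomes unrelated to class assignment in D+E, and the unadjusted test keeps its level. The sizes above apply to a narrower null: class or leader effects exist in D+E but average to zero. This objection is accepted in full.

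**The ICC may be small.** No section describes closed classes with fixed membership. Forsyth participants choose their location. Half of the scheduled diet contacts in months 0-12 are individual, and all are in months 13-18. Walking is individually prescribed, one weekly exercise session need not be at a centre, and phone, email and virtual delivery can substitute. All this may lower the ICC or mix class membership. Controls also meet in groups, so clustering in D+E only is a simplification. These points support the lower rows of the table but do not make independence a given.

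**Venues as clusters.** A reader might go further and treat the six named venues, about 55 analysed participants each, as random clusters. At ICC 0.02 that gives 81.5% power by the normal approximation, but only about 11 degrees of freedom, about 74% power on that basis and an interval about 40% wider. Six venues are too few to support such a model, and they could equally be viewed as fixed. The point does not rest on that scenario.

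**Conclusion.** The point holds as an omission. The treatment is delivered in groups mainly in one arm, nothing in the model or the sample-size calculation allows for that, and no other section corrects it. The 94% is not miscalculated; it is the figure for no clustering.

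The size depends on two quantities that the documents do not give. Over classes of 8 to 20 and ICC 0.01 to 0.05, with clustering in D+E only, the test of a zero average effect would run at about 5.4% to 10.7%. Power would be about 93% down to 81% with small-sample degrees of freedom (93.6% to 83.0% by normal approximation). At ICC up to 0.02 the consequence is modest: size at most about 7.2% and power about 89% or more. Even the worst assumed case leaves power near the lowest value in the plan's own Table 1 (81%). This is therefore an inexpensive improvement to the analysis plan and not a reason to doubt the sample size.

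**What to change.** 1. Record each D+E participant's class, or main interventionist, as first assigned. Using the first assignment keeps later switching from redefining the clusters.
2. Prespecify, as a named sensitivity analysis to the primary 18-month contrast, the same mixed model with a class-level random effect in the D+E arm only and small-sample degrees of freedom. Report the ICC with its interval.
3. Limit the variance sentence in Primary Aim to the stratification factors.
4. In Primary Outcomes, state that 94% assumes no clustering and give power over a stated range of ICC and class size.
5. Do not use venue as the random effect.

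The cost is analysis-plan wording, one recorded variable and one additional model; no more participants and no change to treatment. The documents do not say whether class membership is already logged, and it may be hard to recover later. The downside is a somewhat wider interval in the sensitivity analysis, about 3% to 26% over the assumed range, and a less favourable stated power. If the estimated ICC is near zero, the sensitivity analysis simply supports the primary result.

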# Secondary Aims

Repeated measures mixed linear models similar to Aim 1 will be used to analyze WOMAC function, 6-minute walk, and SF-36 physical subscale. Each outcome will be modeled separately, and 18-month effectiveness will be tested based on a two-tailed significance level of 0.05. The model will include the fixed effects study arm, time, time-group interaction, county, gender, baseline BMI, and baseline values of the outcome; participant ID number will be included as a random effect, and an unstructured covariance will be used assuming model convergence is not a problem (AR[1] otherwise). Preliminary analyses will be conducted to check the shape of the distributions and variances between groups and as a function of the covariates. Regression diagnostics and residual plots will help to find appropriate transformations, if necessary.

# Missing Data

If missing data are related to outcomes, our results could be biased. Our models will include variables from previous visits determined to predict loss to satisfy Little and Rubin's conditions for data considered missing at random (MAR). If "informative censoring" occurs, we will compare analyses using subjects with complete data, multiple imputations, or explicit modeling of the censoring mechanism (Conaway, 1993, Wu and Bailey, 1989).

## **Primary Outcomes**

Aim 1. A total sample of 820 (410/group) will provide 94% statistical power to detect differences  $\geq 15\%$  in pain at the 2-sided 0.05 significance level with 80% retention (2-sample t-test, Nquery Advisor). Based on ADAPT (Messier et al). The D+E group in IDEA reduced pain by an average of 51%. This approach utilizes the conditional variance approach of Borm et al. for the estimation of power for ANCOVA models using group standard deviation  $\sigma = 3.50$ , Pearson correlation between baseline and 18-month pain score of  $\rho = 0.4$  for a conditional standard deviation  $\sigma_c = 3.21$  ( $\sigma_c = \sqrt{1 - \rho^2} \times \sigma$ ), and 18-month treatment WOMAC pain means ~D+E

Table 2: Detectable absolute a         410/group, 80% retention, 85%         18M values is p .	modifications in retention and treatment effect are				
Variable	Anticipated 18m Control mean*	Standard Deviation	ρ	D+E Mean (% change from C)	presented in Table 1. Correlation
WOMAC Function	17.5	11.5	0.6	15.3 (-12.3%)	between baseline
Mobility: 6-Minute Walk (m)	509	90.7	0.7	524 (3.0%)	and 18 month pain
SF-36 Physical Score (0-100)	42.0	10.1	0.5	44.1 (4.9%)	values are

= 5.03 vs E-only control = 5.92 ( $\Delta$  = -0.887). Variations of anticipated power due to

WOMAC Function17.511.50.615.3 (-12.3%)between baselineMobility: 6-Minute Walk (m)50990.70.7524 (3.0%)and 18 month painSF-36 Physical Score (0-100)42.010.10.544.1 (4.9%)values areestimated from the IDEA trial, while anticipated treatment effects and standard deviation for painwere obtained using weighted averages of D+E and non-D+E treatments from the ADAPT andIDEA studies, with some attenuation of the anticipated treatment effect due to the pragmatic

nature of WE-CAN (Table 1).

 Table 1: Power estimates for WOMAC pain, assuming baseline N=820, correlation between BL and 18 months=0.4, and common group SD = 3.50.

18 month Control Mean WOMAC	18 Month D+E WOMAC Pain (% difference from	18-Month Retention						
Pain	Control)	70%	75%	80%	85%			
		Power						
	5.15 (13%)	81%	84%	86%	88%			
5.00	5.03 (15%)	91%	92%	94%	95%			
5.92	4.91 (17%)	96%	97%	97%	98%			

## Secondary Outcomes

*Aim 2.* Our sample size provides a moderate effect size of 0.234 at 85% power with relevant detectable differences. However, all estimates from IDEA and ADAPT were collected under rigorously controlled conditions; therefore the estimates for the pragmatic trial are conservative. We assume in Table 8 a total baseline sample size of N=820, 80% retention at 18 months, and a 0.05 level of significance for all tests. The detectable and % differences from control aim to achieve 85% power. The mean differences in WOMAC function for D+E compared to D only and E only in IDEA were -3.3 and -4.3, respectively. Likewise, the differences in 6-minute walk distance for the D+E group versus D only in IDEA and ADAPT (41.5 and 42.1, respectively) indicate that the mean difference to achieve 85% power (15.2 m) is modest. IDEA indicated that SF-36 physical subscale was significantly improved in the D+E arm, with an observed difference of 2.8 compared to E alone (Table 2).

References:

**The ARIC investigators.** The Atherosclerosis Risk in Communities (ARIC) Study: design and objectives. Am.J.Epidemiol. 1989 Apr;129(4):687-702.

Brooks R (1996). EuroQol: the current state of play. Health Policy 37(1):53-72.

Campbell PT. Obesity: a certain and avoidable cause of cancer. Lancet. 2014;384(9945):727-8.

